The overall goal of this project is to provide feasibility data for a novel method of defining patient-specific functional anatomic targets for GPi DBS placement.

Aim 1. To evaluate the feasibility of a novel, clinically applicable 3 Tesla (3T) MRI protocol for functional segmentation of the GPi based on connectivity measures derived from MRI diffusion-weighted imaging.

- a) Assess the ability of spatially localizing the motor functional representation within the GPi in individual subjects with a clinically feasible imaging protocol using widely available 3T MRI.

Aim 2. To determine the variation in degree of overlap between the traditional atlas-based target point and the derived MRI functional segments on pre-operative imaging

- a) To better understand the relationship of the traditional target point and the functional segments, we will compare the degree of overlap. We hypothesize that the traditional target point will show variation between subjects in the degree of overlap with each functional segment suggesting inadequacy of structural targeting methods that are based on generalizations rather than patient-specific functional targets

Aim 3. To compile preliminary evidence for the role of a patient-specific, functional-based targeting protocol to replace potentially inaccurate atlas-based methods in treating Parkinson's disease that can be implemented on commonly available 3T MRI scanners

- a) Based on the stimulation parameters used to achieve a satisfactory treatment response, a model of the volume of activated tissue will be generated. The degree of overlap between this volume of tissue will be assessed on both the pre-operative functional target and the original atlas-based target. We hypothesize that the volume of activated tissue will closely overlap with the functional segment most connected to the motor and pre-motor cortex.
- b) Current data will be the basis for pursuing additional funding for implementing the 3T protocol in a larger patient cohort to further explore the potential role in treatment targeting
- c) Eventual long-term goal will be acquisition of external funding for a clinical trial using the targeting sequence prospectively to assess the overall goal of this investigation: improving success rate and decreasing complication rate by addition of patient-specific functional targeting of the GPi.

II. Background and Significance

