Only one prior study has attempted to provide GPi segmentation based on structural connectivity in normal subjects.³ The authors found inconsistent results with the segmentation scheme. We believe our design to have advantages over this prior study for two primary reasons: (1) differences in the MRI data acquisition and (2) our selection of target regions for the segmentation. In contrast to this prior study, we have focused our target regions to better fit with the expected connectivity profile of the GPi based on known histologic data.

If the aims of this pilot are achieved, we will have sufficient evidence to show the feasibility of a clinically applicable MRI protocol for reliably localizing the patient-specific functional target within the GPi, rather than solely from a structural standpoint. By modifying inaccurate atlas-based methods, we hope to improve the accuracy of localization of the specific functional region of the GPi for treatment of PD that would be personalized to each individual patient.

Our long-term goals are to evaluate patient outcomes relative to our targeting methodology and subsequently pursue prospective clinical trials with the hypothesis that our connectivity-based targeting method increases success rates and decreases complications compared with traditional atlas-based methods. If our pilot is successful, we aim to pursue extramural funding for validation of the methodology in pre-operative targeting.

III. Progress Report and Preliminary Studies

The strategies utilized in the proposed project are similar to segmentation strategies previously applied to the human thalamus.⁴ In previous work, we also have shown that the thalamus can be segmented based on probabilistic tractography measures to pre-defined cortical regions of interest. We have also illustrated that significant variation exists with regards to the functional localization of current atlas-based stereotactic targets within the thalamus (Figure 1). This work has yielded an accepted abstract at a national meeting and manuscript currently under review. The basic methodology utilized in prior work will be applied to the current project. Necessary modifications include re-defining the connectivity targets.

[figure not shown]

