Figure 1. Axial (top) and sagittal (bottom) images of (A) the areas most connected to the supplementary motor area/premotor cortex (blue), primary motor cortex (red), and primary sensory cortex (green) compared to the coordinate-based ventral intermediate thalamic nucleus (Vim) deep brain stimulator target (white circle). Statistical heat maps for probability of connectivity to (B) supplementary motor area/premotor cortex, (C) primary motor cortex, and (D) primary sensory cortex relative to the coordinate-based Vim deep brain stimulator target (blue circle). (Heat map thresholds are 5-100%)

In addition, we have analyzed a small cohort of patients with GPi placement retrospectively (Figure 2). Unfortunately, the existing data is of insufficient quality to achieve the goals of the current project; however, this data does establish some feasibility of the proposed pilot.

[figure not shown]

Figure 2. Sagittal, coronal, and axial images show segmentation of the globus pallidus internus. The DBS lead is positioned within the segment most connected to the primary motor cortex (yellow).

A foundation of success in the proposed project is the acquisition of high-quality data, as well as utilization of pre-processing and processing methodology that maximizes connectivity measures. I have gained significant experience in many of these methodologies, such as multiband EPI and connectivity analysis, as a co-investigator and the head of data quality and

acquisition in a grant utilizing the Human Connectome Project protocol (Human Connectome Project - Connectomes Related to Human Disease: Changes in Visual Cortical Connectivity Following Central Visual Field Loss. Project Number: U01-EY025858-01A1. PI: [name].).

Experience with the translation of advanced neuroimaging techniques to neurosurgical intervention is also beneficial to the proposed project. An understanding and appreciation of the limitations of various neuroimaging procedures in the clinical setting is essential for future adaptation to surgical guidance. In addition to my experience in clinical functional neuroimaging, I have authored or co-authored multiple papers in neurosurgical application of advanced neuroimaging techniques, including diffusion MRI.⁵⁻¹⁰

IV. Research Design and Methods

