e. Data Handling - All data will be collected in an anonymized fashion with unique coded identifiers for each subject. The identifier linking to the patient will be stored in a separate password-protected spreadsheet for purposes of collecting data at each of the timepoints in the study.

Clinical data will be tabulated within an Excel spreadsheet that is also password protected and recorded by anonymized ID. The imaging data will be downloaded from the MRI scanner on an encrypted drive and transferred to a password-protected and encrypted Mayo Clinic computer only accessible to the PI. Imaging data will be collected and stored without patient identifiers, only by unique study ID. Processing of the imaging data will be performed and saved on the computer.

f. Data Analysis - MP-RAGE structural scans will be coregistered to the diffusion data and automatically segmented into regions of interest using FreeSurfer software. Regions of interest will consist of: (1) prefrontal cortex, (2) supplementary motor area, (3) premotor cortex, (4) primary motor cortex, (5) putamen, (6) caudate, (7) thalamus, (8) globus pallidus externus, (9) pedunculopontine nucleus, and (10) subthalamic nucleus.

The diffusion data will be used to determine voxel-wise diffusion parameters using a Markov Chain Monte Carlo sampling in the FMRIB Software Library (FSL) “bedpostx” function. A multi-fiber approach (2 fiber orientations) using a multi-shell model will be used. To perform GPi segmentation based on structural connectivity, we will utilize a probabilistic tractography method by way of FSL’s “probtrackx” to calculate probability of connection of each GPi voxel to the predefined volumes of interest (above). Each GPi voxel will then be assigned to the one target with the greatest number of propagated paths by using FSL’s “find_the_biggest” function.

Using the MP-RAGE and FGATIR MRI data, the target point for DBS placement will be determined using current standard of care. The amount of overlap between this target and each of the GPi functional segments will be calculated.

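### Aim 2a reads between-subject variation in target–segment overlap as a sign of inadequate structural targeting, but the plan never estimates segmentation error, so the variation cannot be attributed to anatomy

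*Combined protocol and SAP*

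**What the plan says.** **Inference.** Section I, Aim 2a, expects that the "traditional target point will show variation between subjects in the degree of overlap with each functional segment suggesting inadequacy of structural targeting methods".

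**Measurement.** Section IV.f runs Markov chain Monte Carlo sampling of voxel diffusion parameters, then uses probtrackx to "calculate probability of connection of each GPi voxel to the predefined volumes of interest". Next, "Each GPi voxel will then be assigned to the one target with the greatest number of propagated paths". For Aim 2, "The amount of overlap between this target and each of the GPi functional segments will be calculated". No target radius, overlap formula or error term is given.

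**Data.** Section IV.d plans diffusion imaging (1.5 mm isotropic voxels) before surgery only. The post-operative scan is a T1 MP-RAGE for locating the lead. Section IV.c sets ten subjects, with no statistical basis claimed.

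**Expected reliability.** Section II says that success would show feasibility of a "clinically applicable MRI protocol for reliably localizing the patient-specific functional target within the GPi". It reports that the one earlier connectivity-based GPi segmentation study gave inconsistent results, and expects to do better partly through "differences in the MRI data acquisition" and partly through its choice of target regions. It leaves validation of the method to later extramural funding. Section III judges the team's own retrospective GPi data too poor for this project's goals.

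**Limitations.** Section IV.i covers study size, few poor outcomes and short follow-up. It does not mention segmentation error.

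**The concern.** With one segmentation per subject, the spread of overlap across subjects is the sum of true differences and error in placing segment borders. Nothing in the plan separates the two. The Markov chain step does model uncertainty at voxel level, but the winner-takes-all label discards it, and nothing carries it to the borders or the overlap.

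The direction of the bias matters. Aim 2a counts more variation as more support, so a poorly performing segmentation would tend to look like a stronger case against the atlas target. Aim 3b makes these data the basis for seeking further funding, and Section IV.c wants them to inform the size of later studies. A variance containing an unknown share of error is a weak input to both.

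**Working it through.** **The plan's own figure.** There is none to reproduce. Ten subjects is given without an effect size, SD, alpha or power.

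**1. What can be estimated.** Observed variance of overlap = anatomical variance + error variance. One segmentation per subject estimates only the sum.

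**2. How large the error part could be.** The documents give no border error, target radius or distance to a border, so these are assumptions:
- all subjects have identical anatomy;
- the target is a sphere of radius r = 2 mm;
- the segment border is a flat plane that shifts rigidly, with normal error of SD 0.75 or 1.5 mm (half or one voxel at the stated 1.5 mm).

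The fraction of the sphere on the segment's side of the border, with the border at distance d from the centre, is 0.5 + 0.75(d/r) − 0.25(d/r)³, with d/r limited to −1 to 1. Taking d as normal around the true distance gives this SD of overlap, in percentage points:

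| True distance, target centre to border | Error SD 0.75 mm | Error SD 1.5 mm |
|---|---|---|
| 0 mm (through the centre) | 24 | 36 |
| 1 mm | 19 | 32 |
| 1.5 mm | 14 | 28 |
| 2 mm | 9 | 23 |
| 3 mm | 2 | 13 |
| 4 mm | 0.2 | 6 |

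All of this spread is spurious, because anatomy was held identical. At every distance the larger error gives the larger spread.

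**3. Why the radius must be stated.** At 2 mm from the border, the SD is 6–25 points for r = 1 mm, 7–24 for 1.5 mm, 9–23 for 2 mm and 10–21 for 3 mm. Voxel count matters as well. One voxel is 1.5³ = 3.375 mm³, so a sphere holds (4/3)πr³ / 3.375 voxels: about 1.2, 4.2, 9.9 and 33.5 for r = 1, 1.5, 2 and 3 mm. One relabelled voxel then moves overlap by about 81, 24, 10 or 3 points.

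**4. What two half-data segmentations would give.** With n = 10, within-subject variance is Σ(difference²)/(2 × 10) on 10 degrees of freedom, and the between-subject SD has 9. Normal-theory 95% limits are:
- within-subject SD: √(10/χ²) gives 0.70 to 1.75 times the estimate;
- between-subject SD: √(9/χ²) gives 0.69 to 1.83 times the estimate.

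Overlap is bounded at 0 and 100%, so these limits are approximate. They are wide, but the present plan gives no estimate of error at all.

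**The case against.** The strongest reply is that this is a ten-subject feasibility pilot. The aim says only that variation is suggestive, study data do not guide care (Section V), and validation is openly deferred. That stands, and it sets the limit of the point. A reader might infer that the Aim 2 variation is mostly noise, or that the pilot is invalid. The documents support neither: they give no error figure, and the calculation runs from 0.2 to 36 points on assumed inputs.

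The model can also be challenged. A rigidly shifting border makes all errors along it fully correlated; less correlated voxel errors would partly average out within the sphere and give smaller SDs. The largest figures apply only when the border passes through the target centre, not whenever it cuts the target.

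A reader might also infer that the team has no target definition and no continuous measure. That goes too far. Section III says "The basic methodology utilized in prior work will be applied to the current project", and the Figure 1 legend describes a circular thalamic target and heat maps of connection probability relative to it. The text gives no radius and the figure could not be seen, so any scale on it is unknown. Section IV.f, however, specifies only overlap with segments for Aim 2.

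Aim 3 adds a comparison with activated tissue and clinical change, but it uses the same segments and does not measure their error.

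Finally, a split-half check cannot prove that variation is anatomical, because error common to both halves looks the same as anatomy. That is correct, and it is why the check should be descriptive.

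**Conclusion.** The point holds as a limit on the Aim 2 conclusion. As planned, variation in overlap cannot be divided between anatomy and segmentation error, and the inference rewards noise. Under the assumptions listed (2 mm sphere, border-error SD 0.75–1.5 mm, rigid flat border, identical anatomy), the spurious SD is 24–36 points with the border through the target centre, 19–32 at 1 mm, 9–23 at 2 mm, 2–13 at 3 mm and 0.2–6 at 4 mm. Which of these applies is unknown, because neither the error nor the distance is stated or measured. Even variation that was wholly anatomical would show that the target falls in different segments, not by itself that structural targeting is inadequate. The feasibility purpose of the pilot is unaffected. The change is worth making because it corrects a rule of inference rather than adding detail.

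**What to change.** 1. **Reword Aim 2a and Section IV.i.** For example: *Between-subject variation in overlap will be reported descriptively. On its own it will not be called evidence that structural targeting is inadequate, because it includes segmentation error.* Add segmentation error to the limitations.

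2. **Add a split-half check on the existing diffusion data.** Rerun the segmentation on two halves of each subject's set, for example half the directions in each shell. Splitting by phase-encoding direction is suitable only if both carry the full set of directions. Report the within-subject difference in overlap itself and in primary-motor connection probability, plus Dice for the primary-motor segment. Show these beside the between-subject spread, with 95% intervals and no pass/fail threshold. Call the result a partial estimate: half-data maps are noisier than the full-data maps used for Aim 2, while error shared by the halves (session, parcellation, registration, target placement) is missed.

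3. **State the target radius.** Also report primary-motor connection probability at the target, which probtrackx already yields, and each subject's distance from the target to the nearest segment border.

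**Cost.** No new imaging. There are 10 × 2 = 20 extra segmentation runs if one GPi per subject is analysed; the documents do not say, and there would be more if both sides need separate runs. At the protocol's figure of about one week of processing per subject, 20 runs take at most about 20 processing weeks, and less if parcellation and lead localisation are not repeated. Estimates from ten subjects will be imprecise, and the Aim 2 conclusion will be more cautious. Items 1 and 3 cost little and can be adopted even if the reruns cannot.

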a. Study Design or Overview - Patients selected to undergo GPi DBS placement will be eligible for enrollment in the study. In addition to standard-of-care tests, subjects will undergo an MRI consisting of the proposed novel imaging protocol prior to placement of DBS. The patient will subsequently undergo standard-of-care therapy for DBS placement. Once the stimulator has been programmed post-operatively, the stimulation parameters and corresponding clinical changes will be collected and used to model the volume of activated tissue. The patient will additionally undergo a follow-up MRI used to localize the electrode within the brain to further localize the volume of activated tissue.

b. Study Subjects - Patients presenting to Mayo Clinic Neurosurgery identified to undergo deep brain stimulator placement in the GPi will be identified as potential subjects. Exclusion criteria for the proposed study would be any patient with contraindication to 3 Tesla MRI.

c. Sample Size - Due to the lack of any adequate preliminary studies, a sample size is estimated without statistical basis. A sample size of ten was chosen based on expected recruitment possibilities and sufficient size to prove feasibility and estimate power size for subsequent studies.

d. Data Collection -

Pre-Operative: Relevant clinical information will be collected including demographic data (age, gender), duration of Parkinson's disease, medication history, and a Unified Parkinson Disease Rating Scale (UPDRS) score. Pre-operative MRI will consist of a robust, multi-shell diffusion sequence at high resolution (1.5 x 1.5 x 1.5 mm voxel; b =1000, 2000; 64-directions, AP and PA phase encoding). Additional routine structural imaging consisting of T1-weighted MP-RAGE and FGATIR will also be obtained for purposes of identifying targets for segmentation.

Post-Operative: Clinical data will consist of post-treatment UPDRS score, complications related to DBS placement (e.g. infection, hemorrhage), and the stimulation parameters (voltage and contacts used) from the DBS programming to go with the tremor scoring. Stimulation parameters will also be recorded for any DBS programming that resulted in adverse effects, as well as the effect elicited. The patient will undergo an additional post-operative MRI using a T1 MP-RAGE sequence for purposes of localizing the final lead position.

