The postoperative MRI scan will be coregistered to the pre-operative scans. The final location of the DBS lead will be calculated using LEAD-DBS software. Based on the stimulation parameters, the volume of activated tissue will be calculated with respect to lead localization. The amount of overlap between the volume of activated tissue (VAT) and each GPi segment will be calculated. Linear regression analysis will be performed to determine the degree of improvement in tremor score and degree of overlap between the VAT and each GPi segment. We hypothesize greater overlap between the VAT and GPi segment maximally connected to the primary motor cortex will result in a greater improvement in clinical improvement.

g. Feasibility and Time Frame – The expected timecourse for the study is one year. We would anticipate ~25 patients per year to be potential subjects based on historical figures of number of GPi DBS placements done at Mayo Clinic Florida. The timetable for each individual subject should be <6 weeks. Processing time for each subject is expected to be ~1 week. Since the study is incorporated into current standard-of-care clinical workflow (e.g.

imaging prior to surgery and followup imaging at time of return clinical visit), we anticipate high subject retention.

h. Strengths – The strength of the study lies in the robust diffusion sequence obtained by way of the recently released “multiband” diffusion MRI sequence. This allows a substantial improvement in resolution and data quality compared to traditional methods. Additionally, the prospective nature allows us to collect not only optimal therapeutic DBS stimulation parameters, but also those which produce unintended side effects. By capturing this additional data, it will help us to shed light on the cause of these unintended effects and potentially improve the pre-operative functional targeting. Lastly, the significant experience of the investigators in functional neuroimaging and deep brain stimulation is a significant benefit in preparing the study design and interpreting the data.

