their clinical care. They will also be advised that participating in the study will provide no direct clinical benefits to them. Consent will be obtained as written and verbal consent with the patient. Ten subjects will be recruited.

Potential Risks: This study poses minimal risk to included subjects. The only test/procedure administered that is part of the study and not standard clinical care will be the acquisition of two routine MRI scans. Standard MRI screening precautions will be used to determine patient safety for the MRI environment. Any patients not meeting these standard guidelines will be excluded from the study.

Protection: The primary risk posed to subjects is the risk of MRI. Standard MRI precautions will be exercised to screen patients for any contraindication to MRI. Patients with any safety concerns will be excluded from the study.

Benefits: Subjects will not receive any direct benefit from participation in the study. The data acquired for the purposes of this study will not be used in their clinical decision-making. The benefits gained by the knowledge from our study have the potential of improving current targeting methods for deep brain stimulation and may improve patient outcomes, decrease complication rates, and decrease operating room time.

VI. Gender/Minority Mix

Patients of all demographics will be eligible for the study. No inclusionary or exclusionary criteria will be based on any demographic information.

VII. References:

3. da Silva NM, Ahmadi SA, Tafula SN, Cunha JP, Bötzel K, Vollmar C, Rozanski VE. A diffusion-based connectivity map of the GPi for optimised stereotactic targeting in DBS. *Neuroimage.* 2017 Jan 1;144(Pt A):83-91. doi: 10.1016/j.neuroimage.2016.06.018. Epub 2016 Sep 17.

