** All programming settings will be collected throughout the duration of the study, including intra-operative and peri-operative programming/testing

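### Close overlap of the VAT with the motor segment (Aim 3a) could come from standard lead placement alone, and the plan gives no on-lead reference value to judge it against

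*Combined protocol and SAP*

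**What the plan says.** All places are in the combined protocol and SAP.

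- **Section I, Aim 3a.** "Based on the stimulation parameters used to achieve a satisfactory treatment response, a model of the volume of activated tissue will be generated". Its overlap "will be assessed on both the pre-operative functional target and the original atlas-based target". The hypothesis is close overlap with the segment most connected to motor and pre-motor cortex. The parent aim presents this as preliminary evidence for replacing atlas-based methods, and Aim 3b makes the data the basis for further funding.
- **Section IV.a.** "The patient will subsequently undergo standard-of-care therapy for DBS placement".
- **Section IV.f.** On the structural scans, "the target point for DBS placement will be determined using current standard of care". After surgery, "the volume of activated tissue will be calculated with respect to lead localization". Overlap of the VAT with each GPi segment is calculated, and a linear regression relates improvement in tremor score to that overlap. Here the segment of interest is the one most connected to primary motor cortex.
- **Section V, Benefits.** "The data acquired for the purposes of this study will not be used in their clinical decision-making".
- **Section IV.d and the schedule footnote.** Settings that caused adverse effects are recorded. More broadly, "All programming settings will be collected throughout the duration of the study, including intra-operative and peri-operative programming/testing". Section IV.f specifies no analysis of these additional settings.

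**The concern.** A prediction of close overlap needs a value to be compared with: how much overlap would be seen if the segmentation carried no information about where stimulation works. Aim 3a gives no metric, no threshold and no such value.

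This matters because the lead is already in place, by standard targeting, before the segmentation is compared with anything. If standard targeting tends to land in the motor segment, the VAT will overlap that segment whether or not the segment explains the response. That result would suggest that the existing method already reaches the functional target, which is close to the opposite of what Aim 3 wants to conclude. An overlap figure that fits both readings would then be carried into the funding case for the larger study.

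**Working it through.** The plan has no figure to reproduce. Section IV.c says the sample size of ten has no statistical basis, and no alpha, power or effect size is given. The check is mainly one of logic, with three short calculations.

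**Step 1. What can move the VAT.** The lead goes where standard of care puts it (IV.a, IV.f), study data do not enter care (V, Benefits), and the VAT is modelled from the localized lead (IV.f). Surgery therefore sets the reachable region. Within it, contact and voltage choice move the VAT, and those choices respond to clinical effect. The response-driven part of VAT position lies along the lead, and Aim 3a makes no comparison along the lead.

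**Step 2. How far lead position alone can move overlap (illustration).** All dimensions are assumed; none is in the documents. Take the VAT as a sphere of radius v = 2.5 mm, the motor segment as a sphere of radius R = 3, 4 or 5 mm, and d as the distance between centres. If d + v ≤ R, the share of the VAT inside the segment is 1. Otherwise, for the partly overlapping cases here, the shared volume is

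V = π(R + v − d)²(d² + 2dv − 3v² + 2dR + 6vR − 3R²) / (12d),

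and the share is V divided by (4/3)πv³.

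Put the active contact 1 mm above the segment centre. With the lead through the centre, d = 1. With the lead 4 mm to the side, d = √(4² + 1²) = 4.12.

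| Segment radius | Lead through centre | Lead 4 mm to the side |
|---|---|---|
| 3 mm | 0.91 | 0.11 |
| 4 mm | 1.00 | 0.35 |
| 5 mm | 1.00 | 0.67 |

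Nothing about response enters this table. Overlap runs from low to complete on lead position alone. In the 5 mm case with a central lead, a contact 3 mm from the centre still has a share of 0.95, so a less central contact would also count as close overlap.

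**Step 3. Do the planned comparisons supply the reference?**

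- *Atlas target (Aim 3a).* The standard target also steers the lead, so distance from or overlap with it partly measures surgical accuracy. It is not a neutral reference.
- *Regression on tremor improvement (IV.f).* This uses outcome, but compares patients whose lead positions were not assigned. With n = 10 and two-sided alpha 0.05 (assumed), the critical t on 8 degrees of freedom is 2.306, so the smallest significant correlation is 2.306 / √(8 + 2.306²) = 2.306 / 3.649 = 0.63. Simulated power is 0.33 at a true r of 0.5 and 0.80 at 0.76. Even a clear result would not say what overlap to expect from placement alone.

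**Step 4. What an on-lead contrast could show with ten patients.** For a paired t-test with n = 10 and two-sided alpha 0.05 (assumed), the noncentrality is D√10, where D is the mean difference divided by its SD.

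| D | D√10 | Power |
|---|---|---|
| 0.5 | 1.58 | 0.29 |
| 0.8 | 2.53 | 0.62 |
| 1.0 | 3.16 | 0.80 |

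The 95% confidence interval has half-width 2.262 / √10 = 0.72 SD. The contrast suits estimation in a pilot, not a confirmatory test.

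**The case against.** The strongest reply is that the plan already has two safeguards. IV.f relates overlap to clinical improvement, and lead placement alone would not produce such a relation. Aim 3a also compares with the atlas target; since surgery pulls the lead towards that point, a VAT lying away from it and inside the motor segment would carry some information. Both points stand in part. A reader might infer that the plan never links the segment to outcome or has no comparator at all, and that would be wrong. What remains is that neither safeguard gives a reference value for close overlap.

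A reader might also infer that surgery fixes where the VAT falls, or that every contact on a lead will overlap the motor segment. The documents support neither. Contact and voltage choice still move the VAT. Figure 2 shows a lead inside the primary-motor segment, but it is one illustration from a retrospective cohort whose data section III calls inadequate for this project's goals. Aim 2 itself expects overlap of the target point to vary between subjects.

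There is also a fair objection to an on-lead contrast. If unused contacts lie outside the GPi, their motor overlap is low wherever the segment borders run, so any GPi outline would give a positive difference. Unused contacts that were never tested are also not known to be ineffective. Both points are right and shape the fix.

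Last, this is a ten-patient feasibility study that says it may not reach significance. That limits how serious the point is. It does not make an overlap figure interpretable without a reference.

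**Conclusion.** The concern holds in a limited form. Close overlap under Aim 3a can be met by standard placement alone, so by itself it cannot support replacing atlas-based targeting. This follows from the protocol's own statements on placement, use of study data and VAT modelling, and needs no numerical assumption.

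The size of the effect cannot be taken from the documents. They do not state the number of contacts per lead, how many are active, the VAT size or the segment size. The overlap shares above (0.11 to 1.00) illustrate the range under assumed dimensions and are not predictions. For the same reason, no chance probability for the choice of contact is offered.

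A reader might go further and conclude that the segmentation is uninformative, or that Aim 3 as a whole must fail. The documents do not support that: the outcome regression is a real, though weak, test at n = 10. The gap is one missing reference analysis and the wording of the conclusion. It is worth closing before analysis because the result is meant to support further funding.

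**What to change.** In section IV.f:

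1. For each lead, also model the VAT at the other contacts of that lead, with the settings otherwise unchanged. State in advance how settings that use more than one contact are handled and, if a patient has two leads, average them so that the patient stays the unit.
2. Express overlap as the share of the within-GPi VAT that falls in the prespecified motor segment. Exclude contacts whose VAT lies outside the GPi, so that leaving the GPi does not produce a positive difference by itself.
3. Report the therapeutic-contact value minus the mean of the remaining contacts, as a paired within-patient difference with a confidence interval, labelled exploratory.
4. Where settings at other contacts were actually tested (IV.d and the schedule footnote), report those contrasts separately from the purely modelled ones.

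In Aim 3a, describe absolute overlap as where standard placement lands, not as evidence for replacing the atlas target. Use one motor segment definition throughout: Aim 3a names motor and pre-motor cortex, while IV.f names primary motor cortex only.

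**Cost.** Extra VAT runs per lead, after the lead localization already planned in LEAD-DBS, plus wording. No extra visits, scans or patients, and no change to care. The downside is that a lead wholly inside one segment contributes little to the contrast, and the report should say how many such leads there were. With ten patients only large differences will be distinguishable from zero.
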